15.1.1 Treatment-Emergent Adverse Events

An overview summary of TEAEs will be provided including number of participants who experience at least any

- TEAE
- Related TEAE
- Serious TEAE
- Related serious TEAE
- TEAE by intensity (NCI-CTCAE grades 1-4)
- Related TEAE by intensity (NCI-CTCAE grades 1-4)
- AESI
- Related AESI
- TEAE leading to study termination
- Related TEAE leading to study termination
- TEAE leading to death
- Related TEAE leading to death.

Frequency tables of TEAEs by SOC and PT will be provided for:

- All TEAEs
- TEAEs at frequency threshold of 5%
- Related TEAEs (if any)
- Serious TEAEs (if any)
- Related serious TEAEs (if any)
- TEAEs of special interest (if any)
- TEAEs leading to study termination (if any)
- Related TEAEs leading to study termination (if any)
- TEAEs leading to death (if any)
- Related TEAEs leading to death (if any)

Additionally, a summary table displaying the number of participants with TEAEs by Primary SOC and PT will be provided by worst severity grade. A graphical presentation of TEAEs occurring in >10% of participants will be provided as well.

A listing of all AEs will be provided. The listings will include seriousness, severity grade, relationship with study treatment, if time-emergent, and outcome.

15.1.2 Adverse Events Leading to Discontinuation of Study Intervention

Since the study intervention is administered as single dose treatment on Day 1, discontinuation of study intervention due to AEs or any other reason cannot happen.

15.2 Deaths, Other Serious Adverse Events, and Other Significant Adverse Events

15.2.1 Deaths

A listing of deaths, if any, will be provided including date and cause of death.

15.2.2 Serious Adverse Events

A listing of serious AEs (SAEs), if any, will be provided.

15.2.3 Other Significant Adverse Events

A listing of AESIs, if any, will be provided.

15.3 Disease Related Events

Disease related events (DREs) are captured separately in the same manner as Adverse Events. A listing of DREs, if any, will be provided.

15.4 Clinical Laboratory Evaluation

The following laboratory parameters will be measured during the trial and reported as part of the safety evaluation (for a detailed list of parameters refer to Appendix 10 of the protocol):

- Hematology
- Biochemistry
- Coagulation

Summary tables over time displaying absolute values and changes from baseline will be provided for continuous data. For a graphical presentation line plots of lab parameters standardized to times ULN over time will be provided for each participant. Plots will be grouped by participants of different M5717 doses and by lab parameters in the following way:

- Biochemistry:
 - Alanine Aminotransferase, Alkaline Phosphatase, Aspartate Aminotransferase, Bilirubin
 - Calcium, Creatinine, Glucose, Lactate
 - Potassium, Protein, Sodium, Urea Nitrogen
- Hematology:
 - Basophils, Eosinophils, Ery. Mean Corpuscular Hemoglobin, Ery. Mean Corpuscular HBG Concentration, Ery. Mean Corpuscular Volume
 - Erythrocytes, Hematocrit, Hemoglobin
 - Leukocytes, Lymphocytes, Monocytes, Neutrophils, Platelets, Reticulocytes

- All coagulation parameters

In addition, shift tables from baseline based on normal ranges will be provided.

In order to investigate possible events of Hy's Law, an eDISH Plot will be provided.

Outputs will be presented using the Merck standard lab units (see *Guidance Document Merck Standard Lab Units and Normal Ranges* Version 2.2 for reference) unless otherwise agreed. Normal ranges will be provided by the local laboratories, and out of range flags will be calculated based on the normal ranges. Laboratory data not transferred from the central laboratory in Merck standard units will be converted to Merck standard units before processing. Both original units and SI units will be provided in the SDTM domain.

Subject Data Listings will only be provided for subjects with abnormal test results (lower than LLN and higher than ULN, abnormal CS and abnormal NCS).

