Visit Number	SCR	Visit 1	Visit 2	Visit 3	Visit 4	Visit 5	Visit 6	Visit 7	Visit 8	Visit 9/ EOS			
Day	Day 1 (-12h) b	Day 1 (Dosing)	Day 2	Day 3	Day 4 (72h post) c	Day 8	Day 15	Day 22	Day 29 d	Day 43			
Visit Window	-	-	-	-	-	± 1 day	± 2 days	± 2 days	± 2 days	± 2 days			
Hematology, coagulation, chemistry, and urinalysis	X			X		X			X		X	AT follow-up (chemistry including ALT, AST, TB, and coagulation [optional if suspicion of drug-related ATs increased])	A sample should be collected before rescue treatment administration. If increase in: AT levels $> 3 \times$ ULN and/or TB $> 2 \times$ ULN, confirmation of abnormality will be required within 48-72h including ALT, AST, ALP, and TB, and afterwards weekly follow-up will be required at minimum; if early clinical symptoms of liver toxicity or DILI (e.g., anorexia, nausea, fatigue, right upper abdominal discomfort, vomiting) are present, the Investigator should start the same follow-up protocol indicated previously when any increase of AT and TB is present, unless there is an alternative explanation for the clinical symptoms and the liver enzymes increase.
Randomization		X											
Dosing		X	X h	X i									h Day 2 dosing applicable for Cohort B2 (2-day) in

Assessments & Procedures		Hospitalization					Out-patient Visits					Unscheduled Visit a	Notes
Visit Number	SCR	Visit 1	Visit 2	Visit 3	Visit 4	Visit 5	Visit 6	Visit 7	Visit 8	Visit 9/ EOS			
Day	Day 1 (-12h) b	Day 1 (Dosing)	Day 2	Day 3	Day 4 (72h post) c	Day 8	Day 15	Day 22	Day 29 d	Day 43			
Visit Window	-	-	-	-	-	± 1 day	± 2 days	± 2 days	± 2 days	± 2 days			
Temperature	X	X	X	X	X	X	X	X	X	X			The exact assessment timepoints during the hospitalization period are provided in Table 2 .
Adverse events		←===== Continuous =====→											
Concomitant medications	X	X	X	X	X	X	X	X	X	X			
Rescue treatment			As required										Rescue malaria treatment to be administered beginning Day 43 in Part A or as required.
Assessments only performed if the participant has been enrolled:													
Malaria and severe malaria signs and symptoms	X	X	X	X	X	X	X	X	X	X			
Blood films (microscopy)	X	X	X	X	X	X	X	X	X	X			Thick and thin blood films will be collected at Screening to confirm inclusion/exclusion criteria.

Assessments & Procedures		Hospitalization				Out-patient Visits					Unscheduled Visit a	Notes

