## Appendix 5 Liver Safety: Suggested Actions and Follow-up Assessments

The DILI will be defined as following:

- An elevated ALT or AST  $> 3 \times$  ULN. Often with ATs much greater: 5 to  $10 \times$  ULN.
- An elevated ALT or AST  $> 3 \times$  ULN plus serum TB  $> 2 \times$  ULN, without findings of cholestasis (defined as serum ALP activity  $< 2 \times$  ULN).
- No other reason can be found to explain the combination of increased AT and serum TB, such as viral hepatitis, alcohol abuse, ischemia, preexisting liver disease, or another drug capable of causing the observed injury.

An increase of serum ALT or AST to  $> 3 \times$  ULN should be followed by repeat testing within 48 to 72 hours of all four of the usual serum measures (ALT, AST, ALP, and TB) to confirm the abnormalities and to determine if they are increasing or decreasing. The need for prompt repeat testing is especially great if AT is much  $> 3 \times$  ULN and/or TB is  $> 2 \times$  ULN.

If symptoms persist or repeat testing shows AT  $> 3 \times$  ULN for participants with normal Baseline measures, it is appropriate to initiate close observation to determine whether the abnormalities are improving or worsening.

Close observation includes:

- Repeating liver enzyme and serum bilirubin tests 2 or 3 times weekly. Frequency of retesting can decrease to once a week or less if abnormalities stabilize and the participant is asymptomatic.
- Obtaining a more detailed history of symptoms and prior or concurrent diseases.
- Obtaining a history of concomitant drug use (including nonprescription medications and herbal and dietary supplement preparations), alcohol use, recreational drug use, and special diets.
- Ruling out acute viral hepatitis types A, B, C, D, and E; autoimmune hepatitis; NASH; hypoxic/ischemic hepatopathy; and biliary tract disease.
- Obtaining a history of exposure to environmental chemical agents.
- Obtaining additional tests to evaluate liver function, as appropriate (e.g., INR, direct bilirubin).
- Considering gastroenterology or hepatology consultations.

All study participants showing possible DILI should be followed until all abnormalities return to normal or to the Baseline state.

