9.3 Presentation of Tables/Listings/Figures

Tables and Figures will be presented by Part, unless otherwise specified. A “Total” column will be included in non-efficacy tables. In the individual participant data listing all individual data will be listed as measured. Unless otherwise specified, all listings will be sorted by Part, M5717 dose, subject ID, and scheduled time point.

Repeated and unscheduled measurements included in the listings will not be used for statistical analyses or summaries, unless the repeated measurement was performed due to unreliable values/technical reasons, e.g., clotted samples. They will be flagged as such in the listings.

Presentation of continuous and qualitative variables

Unless otherwise specified, continuous variables will be summarized using descriptive statistics, i.e., the number of participants with non-missing values (n), the number of participants with missing values (nmiss), mean, standard deviation, median, 25th percentile (Q1) and 75th percentile (Q3), minimum, and maximum.

Qualitative variables will be summarized by frequency counts and percentages. Unless otherwise stated the calculation of proportions will be based on the number of participants of the analysis set of interest. Therefore, counts of missing observations will be included in the denominator and presented as a separate category.

Descriptive statistics by nominal visit or time point, e.g., for laboratory measurements, will include only data from scheduled visits.

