9.4 Analysis visit windows

Each participant will be followed up till Day 43 (\pm 2 days) or the day of premature discontinuation, including 4 continuous days (72 hours post first dose) in the hospital after admission, followed by 5 out-patient visits on Days 8, 15, 22, 29, and 43 (or day of premature discontinuation).

The time window is \pm 30 minutes for each scheduled timepoint on Day 1 through Day 4. The visit window is \pm 1 day for Day 8 and \pm 2 days for Days 15, 22, 29 and 43.

In case any assessment occurs outside of the defined timepoint/visit window, it will be allocated to “unscheduled”. These visits will not be included in descriptive statistics by nominal visit or time point and will be flagged in subject data listings. In case too many measurements are observed outside of the defined visit windows, it will be decided on an individual basis whether those can be allocated to scheduled visits in a reasonable manner during data review before database lock.

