15.6 Other Safety or Tolerability Evaluations

15.6.1 ECG Evaluations

The following analyses will be performed for each 12-lead ECG parameter (RR, PR, QRS, QT, ventricular rate -denoted as HR in what follows-, and QTcF):

- Descriptive statistics at baseline, at each post-baseline time point and changes from baseline at each post-baseline time point
- Frequency (number and percentage) of participants with notable ECG values according to the following categories by analysis visit.
 - QT/QTcF >450 ms, >480 ms, >500 ms
- ECG interpretation (normal, abnormal/not clinically significant, abnormal/clinically significant) will be summarized at Baseline and during the on-treatment period.

- A graphical display, boxplots of change from baseline for ECG parameters will be provided in addition.

Complete ECG profiles will be provided for participants with at least one notable ECG value (related to ECG interpretation) as defined above (i.e. abnormal clinically significant, abnormal not clinically significant). For these participants, all ECG parameter values collected during the study will be provided.

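### Read literally, SAP 9.3 keeps off-schedule liver follow-up tests out of the eDISH plot and shift tables, because SAP 15.4 makes no exception to it

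*SAP*

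**What the plan says.** SAP 9.3 sets a general rule: "Repeated and unscheduled measurements included in the listings will not be used for statistical analyses or summaries". Its one exception applies "unless the repeated measurement was performed due to unreliable values/technical reasons, e.g., clotted samples". A separate sentence in the same section covers by-visit tables: "Descriptive statistics by nominal visit or time point, e.g., for laboratory measurements, will include only data from scheduled visits". SAP 9.4 extends the unscheduled category: "In case any assessment occurs outside of the defined timepoint/visit window, it will be allocated to" that category, with case-by-case reallocation at data review if too many measurements fall outside their windows.

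SAP 15.4 plans shift tables based on normal ranges and one output aimed at Hy's Law: "In order to investigate possible events of Hy's Law, an eDISH Plot will be provided". It does not say whether the plot uses peak or by-visit values, or scheduled or all records.

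The protocol's Schedule of Activities (Table 1) states, for aminotransferases (AT) above 3 x ULN and/or total bilirubin (TB) above 2 x ULN: "confirmation of abnormality will be required within 48-72h including ALT, AST, ALP, and TB, and afterwards weekly follow-up will be required at minimum". The table places AT follow-up in the unscheduled-visit column, and its footnote names an AT increase as a reason for such a visit. Appendix 5 adds closer observation if symptoms persist, or if repeat testing still shows AT above 3 x ULN in a participant with normal baseline values. That observation includes "Repeating liver enzyme and serum bilirubin tests 2 or 3 times weekly", and the frequency may fall to weekly or less once values stabilise.

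**The concern.** Participants with a liver signal are the ones who generate off-schedule chemistry, and 9.3 sets aside off-schedule chemistry. The eDISH plot looks for AT and TB elevations in the same person. If it is built from scheduled records only, it can miss the enzyme peak, or a bilirubin rise that comes after the enzyme rise.

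The liver is central to this trial's safety question. Protocol 2.3.1 lists overlapping hepatotoxicity with an unknown risk of potentiation. Liver signals are adverse events of special interest (AESIs). Laboratory assessments up to Day 29 belong to the primary safety objective of Part A and to a secondary objective of Cohort B0. The eDISH plot is the only output in 15.4 directed at Hy's Law: the shift tables use normal ranges, and no counts by AT or TB threshold are planned.

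**Working it through.** The plan gives no figure to reproduce. The check is a day count followed by a reading of the rules.

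**Inputs.**
- Scheduled chemistry (Table 1): Screening, Day 3, Day 8 and Day 29. The extracted table is broken, so this is an assumption. One further mark reads as the unscheduled column but could be Day 43. Neither reading puts chemistry between Days 8 and 29.
- Windows (SAP 9.4): Day 8 +/- 1 gives Days 7 to 9; Day 29 +/- 2 gives Days 27 to 31. Day 3 has only a 30-minute tolerance.
- Minimum follow-up (Table 1): trigger day + 2 or + 3, then every 7 days.

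**Follow-up days before the Day 29 window opens on Day 27.**

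| Trigger | Confirmation | Follow-up days | Number inside a chemistry window |
|---|---|---|---|
| Day 8 | + 2 days | 10, 17, 24 | 0 of 3 |
| Day 8 | + 3 days | 11, 18, 25 | 0 of 3 |
| Day 3 | + 2 days | 5, 12, 19, 26 | 0 of 4 |
| Day 3 | + 3 days | 6, 13, 20 | 0 of 3 |

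A participant triggered on Day 3 also has the scheduled Day 8 test, so the longest stretch without scheduled chemistry is Day 8 to Day 29, or 29 - 8 = 21 days. Under Appendix 5 close observation, those 3 weeks would hold 3 x 2 = 6 to 3 x 3 = 9 off-schedule tests.

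Some of these days lie within the windows of the Day 15 visit (Days 13 to 17) or the Day 22 visit (Days 20 to 24): Days 17 and 24 in the first row, Days 13 and 20 in the last. Those visits have no scheduled chemistry, so a liver test taken then is still an unscheduled measurement. The first confirmatory test (Day 10 or 11, Day 5 or 6) falls in no visit window.

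**Applying the rules.** A confirmatory or weekly liver test is repeated or unscheduled, and it is not a technical repeat. The eDISH plot and shift tables are not listings. Section 9.3 therefore excludes the test from both unless 15.4 says otherwise, and it does not. The separate by-visit sentence in 9.3 would be redundant if the general rule covered only by-visit tables. Where the SAP wants a different treatment it says so: 16.1.2 keeps post-dose PK samples taken outside their window.

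**Illustration (values invented).** Day 8: ALT 4 x ULN, TB 1.2 x ULN. Repeat at 72 h (Day 11): ALT 9 x, TB 2.5 x. Resolved by Day 29.
- Scheduled records only: maximum (4, 1.2). TB is below 2, so the point is outside the quadrant defined by AT > 3 and TB > 2.
- All records: maximum (9, 2.5), inside the quadrant.

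At the planned sizes, one such participant is 1/12 = 8.3% of Part A or 1/25 = 4.0% of Cohort B0. These are shares of the cohort and say nothing about how likely the event is.

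**The case against.** The best reply is that 9.3 never names the eDISH plot. Its laboratory-specific sentence, like 9.4, restricts by-visit descriptive statistics, and an eDISH plot shows individual participants. A programmer could reasonably plot peaks over all records. This stands in part: the exclusion is inferred from a general rule. But plotting all records would depart from that rule as written, and the SAP should settle the matter.

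The second reply is that nothing is lost. Unscheduled values stay in the listings with a flag, and laboratory listings cover every participant with an abnormal result. AESIs are tabulated and listed, and 15.4 also plans individual line plots in multiples of ULN. This also stands. A reader might infer that the report would show no Hy's Law case, and the documents do not support that. The remaining weakness is that AESI status depends on a tick on the adverse event form, the SAP does not say whether the line plots include unscheduled records, and a listing does not correct an empty quadrant.

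A reader might also link this to the liver stopping criteria in Protocol 4.1. That link fails: the IDMC judges those criteria during the study, whereas SAP section 6 covers end-of-study data and section 7 records that Cohorts B1 to B3 were not enrolled.

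Nor does the argument carry over to QTcF. SAP 15.6.1 defines that table as "Frequency (number and percentage) of participants with notable ECG values according to the following categories by analysis visit", so limiting it to scheduled visits fits its stated purpose. Complete ECG profiles are provided for participants with an abnormal interpretation, and Table 1 sets no repeat-ECG trigger comparable to the liver rule.

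**Conclusion.** The concern holds as a conflict between a general exclusion rule and an eDISH plot whose input is not specified. Followed literally, the rule omits all 3 minimum follow-up tests before Day 27 after a Day 8 trigger, and 3 or 4 after a Day 3 trigger. The triggering value at a scheduled visit would still be plotted. What can be missed is a later enzyme peak, or a TB rise above 2 x ULN seen only on follow-up. The effect is confined to the eDISH plot and shift tables.

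This rests on two assumptions: that Table 1 schedules no chemistry between Days 8 and 29, and that 9.3 governs figures as well as tables. A point in the quadrant is only a potential case, since Protocol 4.1 also requires no initial cholestasis and no other explanation. The documents give no basis for estimating how often this would happen. The change should be made, because the plot has one purpose and the current rule can defeat it.

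**What to change.** Add to SAP 15.4, as a stated exception to 9.3:

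- The eDISH plot uses each participant's maximum post-dose ALT/AST and maximum post-dose total bilirubin, in multiples of ULN, over all scheduled, repeated and unscheduled records.
- A shift table from baseline to worst post-dose value uses the same records.
- By-visit descriptive tables remain restricted to scheduled visits.

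Leave the by-visit QTcF table as it is. At most, add a separate row for the worst QTcF at any post-dose time.

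The cost is a short SAP insertion, a programming flag and one additional shift table. No new data are needed, and the by-visit tables do not change.

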15.5 Vital Signs

Summary tables over time displaying absolute values and changes from baseline will be provided for the following vital sign parameters:

- Body temperature (°C)
- Systolic and diastolic blood pressure (mmHg)
- Respiration rate (bpm)
- Pulse rate (beats/min)

A listing of all vital signs data will be provided.

15.6 Other Safety or Tolerability Evaluations

15.6.1 ECG Evaluations

The following analyses will be performed for each 12-lead ECG parameter (RR, PR, QRS, QT, ventricular rate -denoted as HR in what follows-, and QTcF):

- Descriptive statistics at baseline, at each post-baseline time point and changes from baseline at each post-baseline time point
- Frequency (number and percentage) of participants with notable ECG values according to the following categories by analysis visit.
 - QT/QTcF >450 ms, >480 ms, >500 ms
- ECG interpretation (normal, abnormal/not clinically significant, abnormal/clinically significant) will be summarized at Baseline and during the on-treatment period.

- A graphical display, boxplots of change from baseline for ECG parameters will be provided in addition.

Complete ECG profiles will be provided for participants with at least one notable ECG value (related to ECG interpretation) as defined above (i.e. abnormal clinically significant, abnormal not clinically significant). For these participants, all ECG parameter values collected during the study will be provided.

15.6.2 Malaria Signs and Symptoms

A frequency table per solicited symptom over time will be provided. Total score at each timepoint will also be summarized.

16 Analyses of Other Endpoints/Estimands

16.1 Pharmacokinetics

PK evaluation will be performed by Quantitative Pharmacology, Merck Healthcare KGaA, Darmstadt, Germany, or by a CRO selected by the Sponsor.

16.1.1 Descriptive Statistics of PK Concentration Data

PK concentrations will be descriptively summarized per nominal time point using: number of non-missing observations (n), arithmetic mean (Mean), standard deviation (SD), coefficient of variation (CV%), minimum (Min), median (Median) and maximum (Max).

Descriptive statistics will only be calculated for $n > 2$ in which a measurement of BLQ represents a valid measurement and will be taken as zero for summary statistics of PK concentration data.

Descriptive statistics of PK concentration data will be calculated using values with the same precision as the source data and rounded for reporting purposes only. In export datasets, as well as in the SDTM PC domain, PK concentrations will be provided with full precision and will not be rounded.

The following conventions will be applied when reporting descriptive statistics of PK concentration data:

n 0 decimal place

Mean, Min, Median, Max, SD: 3 significant digits

CV%: 1 decimal place

16.1.1 Descriptive Statistics of PK Parameter Data

PK parameter data will be descriptively summarized using number of non-missing observations (n), arithmetic mean (Mean), standard deviation (SD), coefficient of variation (CV%), minimum (Min), median (Median), maximum (Max), geometric mean (GeoMean), the geometric coefficient of variation (GeoCV), 95% CI for GeoMean.

PK parameters read directly from the measurements (i.e., C_{max}) will be reported with the same precision as the source data. All other PK parameters will be reported to 3 significant figures.

The following conventions will be applied when reporting descriptive statistics of PK parameter data:

n 0 decimal place

Mean, Min, Median, Max, GeoMean, SD, 95% CI for GeoMean: 3 significant digits

CV%, GeoCV%: 1 decimal place

